4.4 Sample size calculation

This sample size calculation is based on our primary endpoint (hand function at 6 months expressed as MHQ score 6 months after injury) and calculated using G Power 3.1.9.2. The MHQ score of an individual without any complaints of the hand is 100. The lowest score, indicating worst pain and severe impairment, is zero. The hypothesis will be assessed using a non-inferiority design. The results from two earlier studies on the subject were used for sample size calculation. [4,5] We used a one-sided significance level of 0.025 and a power of 80% with a standard deviation (SD) of 15, and setting our non-

V7 01-02-2024 12 of 30

inferiority limit at 8. The non-inferiority limit of 8 is based on the previous estimated minimal clinically important difference (MCID) of 15 points, divided by 2 and rounded up to 8. A total of 114 patients will be needed to demonstrate non-inferiority of our hypothesis. Each treatment arm will need 57 patients. Including consideration for a potential 10% loss to follow-up, the total number of patients to be included, set at 114, is multiplied by a factor of 1.10. This results in a total of 126 patients to be included.". The MCID of 15 is based on the average of the MCID's of 23, 13 and 8 for the pain, function and work domains, respectively in patients with carpal tunnel syndrome (CTS). [4] The MCID in MHQ score for patients with thumb injury is not yet investigated. Therefore, we decided to use the MCID of CTS patients.

Considering the uncertain outcome of the control group treatment in terms of MHQ-scores for patients with UCL-ruptures, an independent statistician will assess if the sample size calculation needs adjustment, based on the mean change in MHQ-score and SD in the control group, after half of the patients past their 6-month follow-up (N=28).

V7 01-02-2024 13 of 30

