- When the hand surgeon concludes that there is a firm endpoint (meaning adequate healing of the UCL ligament) cast immobilization is continued for another 2 weeks, until a total immobilization period of 4 weeks is completed. An appointment is scheduled after 4 weeks of cast immobilization.
- When there is no firm endpoint of the UCL or there is doubt about a firm endpoint, patients are scheduled for surgery within 5 working days (switching to usual care; see description usual care).

4) Outpatient clinic visit after 4 weeks of immobilization

The patient visits the hand surgeon. The immobilization cast is removed and replaced for a removable cast, which allows the patient to start exercising. Patients are instructed to start using the thumb for regular daily activities, without putting pressure on it, and start thumb exercises consisting of a combination of opposition and abduction/adduction movements. Patients are advised to repeat the exercises 5-10 times a day. A referral is made to the hand therapist to guide this process. Hand therapy will start within 1 week. The frequency and duration of hand therapy will be determined by the hand therapist. Hand therapists from all hospitals will collaborate to achieve consensus on a treatment protocol. Outcome measures are evaluated in the form of physical examination and surveys. A new appointment is scheduled at 3 months.

- 5) Visit to outpatient clinic at 3 months (standard visit)
 Progression of treatment is evaluated with the patient and expectations are managed.
 Outcome measures are evaluated in the form of physical examination and surveys. A new appointment is scheduled at 6 months.
- 6) Visit to outpatient clinic at 6 months (standard visit)
 Progression of treatment is evaluated with the patient and expectations are managed
 Outcome measures are evaluated in the form of physical examination and surveys. A
 new appointment is scheduled at 12 months.
- 7) Visit to outpatient clinic at 12 months (visit for study purpose)

 Treatment outcome is evaluated for study purposes. Outcome measures are evaluated in the form of physical examination and surveys.

USUAL CARE/COMPARISON

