In theory, surgery in the intervention arm could result in an unexpectedly suboptimal outcome compared to immediate surgery. To determine whether this is the case, an exploratory analysis will be performed by ranking the changes in MHQ in the entire group of patients who (eventually) underwent surgery and comparing the mean rankings. If the mean ranking of the subgroup that eventually underwent surgery in the intervention arm indicates a suboptimal outcome (mean ranking more than 2 different in the direction of worsening to the detriment of the intervention arm), a critical event committee will be established to assess, based on a relevant extract from the patient file, whether direct surgery would have resulted in a different outcome. To increase the uncertainty for the committee and to avoid assessment bias, several directly operated patients from the control group will also be added to the set to be assessed. The qualitative reporting of the CEC assessment will be of a descriptive nature.

V7 01-02-2024 24 of 30

COST EFFECTIVENESS ANALYSIS

This evaluation focuses on the question if the proposed intervention for patients with a complete UCL rupture, including Stener Lesions, using initial nonoperative treatment, is cost-effective compared to operative treatment. The economic evaluation will be performed as a cost-effectiveness (CEA) as well as a cost-utility analysis (CUA) from the societal as well as health care perspectives. [13] The primary economic outcome for the CEA is the costs per unit change in overall hand function and closely relates to the clinical outcome measure. The CEA is performed to enable identification of diagnostic or interventional strategies to be preferred economically in the field of hand surgery. The primary economic outcome for the CUA is the costs per quality adjusted life year (QALY). The CUA is performed to enable priority setting during health care policy making across disease areas and health care settings.

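### The check for harm from delayed surgery compares patients selected for non-healing with all directly operated controls, so a worse rank cannot be attributed to delay, and its committee safeguard is not secured

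*Protocol*

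**What the plan says.** Section 7 (Statistical analysis) of the Protocol allows that surgery in the intervention arm might turn out worse than immediate surgery, and sets up a two-stage check.

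- **Stage 1, the ranking.** The method is "ranking the changes in MHQ in the entire group of patients who (eventually) underwent surgery", followed by a comparison of mean ranks. No adjustment, matching or visit is given.
- **Stage 2, the committee.** If the converted subgroup's mean rank is worse by more than 2, a critical event committee reads a file extract and judges "whether direct surgery would have resulted in a different outcome". The Protocol adds a safeguard: "To increase the uncertainty for the committee and to avoid assessment bias, several directly operated patients from the control group will also be added". It does not say what the extract contains or omits.

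Section 5.1 (step 3 of the intervention) determines who enters the converted subgroup. Cast-arm patients go to surgery after the 2-week re-examination when "there is no firm endpoint of the UCL or there is doubt about a firm endpoint". Under usual care in the same section, every control patient is scheduled for surgery after randomisation, with no such filter.

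Section 7 calls the ranking exploratory and the committee's report descriptive.

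**The concern.** The two groups being ranked differ in more than the timing of surgery. The converted group is formed after randomisation, by response to the cast. The control group also contains the patients who would have healed in a cast; the Summary expects these to be about 9 in 10. The controls who would also have failed a cast are the proper counterpart, and they cannot be identified. A difference in mean rank therefore mixes any effect of delay with any difference in prognosis between non-healers and everyone else.

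The committee stage is meant to resolve this, but its question does not fit the mixed set of files. For a directly operated patient the answer is trivial. For a converted patient it can hardly be given without the treatment course, and the treatment course reveals the arm.

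Section 5.2 says there is no evidence that the delay worsens outcome, so this trial is a chance to supply some. This is the only analysis in the Protocol aimed at that question. There is no DSMB (section 6.11) and no early assessment for efficacy or futility (section 6.7). A signal from this check could be blamed on delay when it is selection, or dismissed as selection when it is real.

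**Working it through.** **Inputs from the Protocol**
- Section 4.4: "We used a one-sided significance level of 0.025 and a power of 80% with a standard deviation (SD) of 15", a margin of 8, and "Each treatment arm will need 57 patients".
- Summary: about 1 in 10 cast patients will need surgery. Section 5.2 cites one series with 15%.
- Section 7: the trigger is a mean rank worse by more than 2.

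**Assumptions, not in the Protocol**
- An SD of 15 applies to MHQ change. Section 4.4 does not say whether its SD is for a score or a change.
- MHQ change is normally distributed.
- Non-healers have a prognostic deficit of a given size whatever the timing of surgery.
- All 57 controls are operated on and evaluable.

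**Step 1. The Protocol's own figure.** A t-based non-inferiority calculation with margin 8, SD 15, one-sided 0.025 and true difference 0 gives 57 per arm (114 in total; power 80.6%). Then 114 × 1.10 = 125.4, rounded up to 126. The trial's sample size reproduces. The delayed-surgery check has no sample size of its own.

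**Step 2. Size of the converted group.** 57 × 0.10 = 5.7, about 6. At 15%, 57 × 0.15 = 8.55, about 9. Take m = 6 converted and c = 57 direct, so N = 63.

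**Step 3. Expected mean-rank difference with no effect of delay.** Let p be the probability that a random control patient has a better change than a random converted patient.
- p = Φ(deficit / (15√2)), with 15√2 = 21.21
- expected difference = N(p − 0.5)

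| Assumed deficit (MHQ points) | p | Expected mean-rank difference |
|---|---|---|
| 3 | 0.556 | 3.5 |
| 5 | 0.593 | 5.9 |
| 8 | 0.647 | 9.3 |

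A deficit of about 1.7 points already gives an expected difference of 2, which is the trigger.

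**Step 4. Spread around those values.** With no difference of any kind, SE = √[N(N+1)/12 × (1/m + 1/c)] = √[63 × 64/12 × (1/6 + 1/57)] = √61.9 = 7.9 ranks. The chance of exceeding 2 is then 1 − Φ(2/7.9), about 40%. Simulation (40,000 runs per setting, zero delay effect) gives about 64%, 84% and 98% for assumed deficits of 4, 8 and 15 points. Across 5 to 9 converted and 57 to 63 direct patients the ranges are 63–68%, 81–88% and 97–99%.

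**Step 5. Visit.** The 3-, 6- and 12-month MHQ assessments are dated from injury (section 6.1). Conversion follows the 2-week re-examination, so converted patients have had less time since surgery at each of these visits. The gap is roughly one to two weeks, and it matters more the earlier the visit. Section 7 does not say which visit the change refers to.

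**Step 6. Committee.**

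| | Directly operated file | Converted file |
|---|---|---|
| Would direct surgery have changed the outcome? | Trivial: direct surgery was given | Needs the 2-week finding and the surgery timing |
| Effect of showing the treatment course | Shows the file is a control | Shows the file is a converted patient |

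Mixing in control files protects against bias only if the extract hides the course, and the question pushes the extract towards showing it.

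**The case against.** The strongest reply is that the ranking is only a screen. It is labelled exploratory, crossing the trigger merely convenes a committee, and the committee's file-by-file question is the Protocol's own attempt to separate delay from a difficult case. No non-inferiority conclusion rests on it. This is right about the weight of the point. It does not repair the comparison: the ranking is introduced as the way to determine whether delayed surgery is worse, with no caveat about selection, and even a fully masked committee would face the same selected group.

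Several stronger readings are tempting, and the Protocol does not support them.

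- **That the committee cannot be masked, or that every added control file would be recognised.** The content of the extract is left open, and a committee charter or SAP not shown here may settle it. Redaction is possible. What stands is that masking is not secured by adding files.
- **That converted patients are more severely injured by construction.** All participants have a complete rupture without a firm endpoint at entry (section 4.2), and conversion also covers mere doubt at 2 weeks. The Introduction reports that patients still symptomatic after casting were treated successfully with surgery, with one exception, at a rate it calls similar to initial surgery. A worse prognosis is plausible but undocumented. That the groups are not comparable follows from the selection rule.
- **That selection would always set off the trigger.** The 3.5, 5.9 and 9.3 are expected values; individual trials scatter widely around them.
- **That the bias must run against the cast arm.** The ranking uses change. A worse injury may start from a lower baseline and show a larger gain, in which case selection could hide real harm.

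**Conclusion.** The point holds in a limited form. Followed exactly, the check cannot attribute a worse mean rank to delay rather than to selection, because about 6 patients chosen for non-healing are set against all directly operated controls without adjustment or caveat. A modest prognostic difference would be enough: deficits of 3, 5 or 8 points give expected differences of 3.5, 5.9 or 9.3 ranks against a trigger of 2, with zero effect of delay. Those deficits and the SD of 15 for change are assumptions. The Protocol gives no prognosis figure for non-healers.

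The outcome is also incompletely defined, since no visit is named. The statement that added control files avoid assessment bias is not supported unless the treatment course is removed from the extract.

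Severity is low to moderate. The analysis is exploratory and descriptive, and the randomised intention-to-treat comparison of the two strategies is unaffected.

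**What to change.** **Comparison**
- Name one visit for the MHQ change, for example 12 months, where the difference in time since surgery matters least.
- Report the baseline-adjusted difference between converted and directly operated patients descriptively, with a CI.
- State that it is confounded by selection and cannot by itself be read as an effect of delay.
- Where available, add a comparison within lesion type taken from the early ultrasound that section 5.1 plans in both arms where feasible, provided the ultrasound records lesion type. Do not match on repair technique: it is determined at operation, after the delay, and may be altered by it.

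**Committee**
- Put one neutral question to every file: is the outcome worse than expected for this injury, and why?
- Remove dates, cast history and the 2-week visit from the extract.
- Include at least one control file per converted patient, and unmask only after scoring. Delay is then considered against scores already fixed.
- If this is not done, delete the statement that the added files avoid assessment bias.

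**Cost.** Changes to Protocol or SAP wording and some file redaction; no change to treatment or visits. Numbers will be small, ultrasound will be missing at some sites, and some selection will remain even within lesion type. That is acceptable for a descriptive analysis that says so.

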If the null hypothesis in this study of nonoperative treatment not being clinically non-inferior at six months is not rejected, but indeed lower costs are associated with nonoperative treatment, then incremental cost-effectiveness ratios will be calculated as the extra savings per extra unit in MHQ score lost or the extra savings per additional QALY lost. If the null hypothesis is rejected, a costs analysis and an outcome analysis will be done as distinct partial economic evaluations. The time horizon will be 12 months. It is expected that effects and costs beyond 12 months are similar for both treatment strategies and that a lifetime time horizon is redundant.

Differences between groups will be assessed after correction for bias and using accelerate non-parametric bootstrapping to account for sampling variability, generating 5,000 replications. Results will be presented graphically by cost-effectiveness planes. Cost-effectiveness acceptability curves will be drawn for various levels of willingness-to-pay per QALY up to €50,000, because higher levels cannot be justified by the maximum observable disease burden in this target group of patients. A scenario analysis will be applied by excluding the productivity losses following sick leave. Subgroup analyses will be performed for patients with a paid job.

Missing cost and effect data will be imputed using multiple imputation according to the MICE algorithm developed by van Buuren. Rubin's rules will be used to pool the results from the different multiply imputed databases. [14]

Measurement and valuation of costs

We will gather data on the use of resources and the related costs regarding health care (e.g. medical specialist, hand-physiotherapist, treatment of complications), productivity losses (absenteeism (sick leave) and presenteeism (lowered efficiency while at work due to sick leave from work and lowered productivity while a work)) and out-of-pocket

V7 01-02-2024 25 of 30

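### The 6-month MHQ non-inferiority test decides whether a cost-per-QALY ratio is computed, which conflicts with the plan's unconditional cost-utility outcome, planes and acceptability curves

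*Protocol*

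**What the plan says.** All of this stands in the Protocol, section 7, under the cost-effectiveness heading, unless noted.

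- **Outcome, no condition attached.** Both a cost-effectiveness and a cost-utility analysis are planned, from societal and health care perspectives. "The primary economic outcome for the CUA is the costs per quality adjusted life year (QALY"), and its declared purpose is priority setting across disease areas.
- **Branch A, non-inferiority shown.** "If the null hypothesis is rejected, a costs analysis and an outcome analysis will be done as distinct partial economic evaluations".
- **Branch B, non-inferiority not shown and non-operative treatment cheaper.** Incremental ratios are calculated as "the extra savings per extra unit in MHQ score lost or the extra savings per additional QALY lost".
- **Branch C, non-inferiority not shown and costs not lower.** No ratio is defined.
- **Displays, no condition attached.** Differences are bootstrapped with 5,000 replications and shown on cost-effectiveness planes. "Cost-effectiveness acceptability curves will be drawn for various levels of willingness-to-pay per QALY", up to €50,000.
- **Effect and horizon.** The horizon is 12 months. QALYs are calculated for each patient as the area under the EQ-5D-5L utility curve from baseline, 2, 3, 6 and 12 months.

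The test that selects the branch is the primary clinical one: MHQ at 6 months, 95% confidence interval against a margin of 8.

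**The concern.** Two sets of instructions cannot both be followed. Separate cost and outcome analyses do not produce costs per QALY. A plane or an acceptability curve needs the joint distribution of cost and effect differences, which distinct partial evaluations do not call for. An analyst whose trial succeeds must decide, with the results in view, which instruction governs.

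The gate also answers a different question from the one it controls. It uses one instrument at one time point and tolerates a loss of up to 8 points. The cost-utility effect is utility accumulated over 12 months. The Protocol's Summary expects about 1 in 10 cast patients to need surgery at the 2-week re-evaluation, which lengthens their treatment by 2 weeks. That can move costs and early utility without showing in MHQ at 6 months.

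Finally, Branch B words its ratios as effect lost. Failure to reject the null hypothesis is not evidence of loss, and the QALY difference may have the opposite sign to the MHQ difference.

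At stake is the cost-effectiveness comparison, which the Summary and section 3 place beside functional outcome in the study's aim and section 2 lists among the secondary objectives.

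**Working it through.** **Inputs (Protocol, section 4.4).** "We used a one-sided significance level of 0.025 and a power of 80% with a standard deviation (SD) of 15". "The non-inferiority limit of 8 is based on the previous estimated minimal clinically important difference (MCID) of 15 points", halved and rounded up. "A total of 114 patients will be needed to demonstrate non-inferiority of our hypothesis". "Each treatment arm will need 57 patients".

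**Reproducing the sample size.** The normal approximation gives n = 2 × (1.960 + 0.842)² × 15² / 8² = 55.2, so 56 per arm. The noncentral-t calculation gives 57 per arm with power 80.6%. The stated 57 and 114 reproduce and are not in dispute.

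**How often each branch is reached.** Let d be cast minus surgery in MHQ at 6 months, normal approximation.

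- SE = 15 × √(2/57) = 2.81.
- Non-inferiority is not shown when d is below −8 + 1.96 × 2.81 = −2.49.
- At a true difference of 0: P(not shown) = Φ(−2.49/2.81) = Φ(−0.887) = 0.187, and P(shown) = 0.813.

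About 81% of trials therefore land in Branch A, without a ratio. The other 19% are an upper bound on trials with a ratio, because Branch B also requires lower costs.

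**Selection on the MHQ estimate.** For true difference δ and c = (−2.49 − δ)/2.81, E[d | not shown] = δ − 2.81 × φ(c)/Φ(c). At δ = 0 this is −2.81 × 0.269/0.187 ≈ −4.03. Other values:

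| True difference | P(shown: no ratio) | P(not shown) | Mean estimate if not shown | Shift from truth |
|---|---|---|---|---|
| +2 | 94.5% | 5.5% | −3.69 | −5.69 |
| 0 | 81.3% | 18.7% | −4.03 | −4.03 |
| −2 | 57.0% | 43.0% | −4.56 | −2.56 |
| −4 | 29.6% | 70.4% | −5.38 | −1.38 |
| −8 | 2.5% | 97.5% | −8.17 | −0.17 |

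These means are over all trials in which non-inferiority is not shown. The further cost condition is not modelled.

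**Carry-over to QALYs.** At a true difference of 0 the MHQ shift is −4.03/2.81 = −1.44 standard errors. The QALY estimate shifts by the correlation between the two estimates times −1.44. The Protocol gives no such correlation, so a range is assumed. The last column assumes a true QALY difference of 0 and comes from simulation.

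| Assumed correlation | QALY shift (QALY standard errors) | QALY difference still favours cast |
|---|---|---|
| 0 | 0 | 50% |
| 0.2 | −0.29 | 39% |
| 0.4 | −0.58 | 27% |
| 0.6 | −0.86 | 15% |
| 0.8 | −1.15 | 5% |

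The last column shows why the wording of Branch B should not presume a QALY loss.

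**The case against.** The strongest reply is that the plan loses less than the branch sentence suggests. Three parts of it stand.

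- A reader might infer that a successful trial would yield no acceptability curve and that joint uncertainty is thrown away. The text does not support that. The bootstrap, planes and curves are promised without reference to any branch. What can be shown is a contradiction, and that Branch A leaves out the ratio.
- A reader might infer that the plan treats QALYs as equal once MHQ is non-inferior. It does not say so: QALYs are calculated for every patient, and Branch A includes an outcome analysis, so both increments could still be reported.
- A reader might take −4.0 as the bias in cost per QALY. It applies only to the 6-month MHQ estimate at a true difference of 0. The Protocol does not say that this estimate is the denominator even of the MHQ ratio, given the 12-month horizon. The shift is small when cast treatment is truly inferior, the case for which Branch B seems to be written.

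It is also fair that a ratio is unstable when the effect difference is near zero, so caution about reporting one after non-inferiority is reasonable. But instability depends on the economic effect difference itself, not on whether a 6-month MHQ interval excludes −8. None of this reconciles the two sets of instructions.

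**Conclusion.** The point holds as an internal contradiction combined with a badly chosen gate. Followed as written, the branch rule drops the named primary cost-utility outcome in the scenario the trial is powered for, about 81% of trials at a true difference of 0. It leaves the ratio undefined when non-inferiority is not shown and costs are not lower. The gap is no wider than that: when non-inferiority is shown, Branch A applies whatever the costs.

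The selection effect is secondary. It is about −4.0 MHQ points at a true difference of 0, about −1.4 at −4 and −0.2 at −8. For QALYs it is 0 to about −1.15 standard errors over assumed correlations of 0 to 0.8.

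The figures rest on 57 evaluable patients per arm, SD 15, normal estimates and no covariate adjustment. The planned adjustment for prognostic factors could lower the standard error and so change the percentages. The primary clinical analysis is unaffected, but the rule should be corrected before results are known.

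**What to change.** Delete the conditional rule in the cost-effectiveness part of section 7 and replace it with text to this effect:

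*Whatever the result of the non-inferiority test and whatever the direction of the cost difference, incremental costs and incremental effects (QALYs and MHQ) over the 12-month horizon will be estimated jointly, using the planned bootstrap and multiple imputation. Results will be reported with the planned cost-effectiveness planes and acceptability curves from both perspectives. The incremental ratio will be given together with the quadrant in which it lies, without presuming that effect is lost.*

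This needs no new data or patients: costs, EQ-5D-5L and MHQ are already collected, and the bootstrap, imputation and displays are already planned. The cost is a wording change and minor extra analysis. The one drawback is that the ratio may be unstable when the effect difference is near zero; the plane and the curve then carry the result.
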